**Table 9: Summary of Censoring Rules for PFS**

Situation	Date of progressive disease /Death or Censoring	PFS Outcome
Documented Progressive Disease or death in the absence of progression	Date of earliest documentation of progressive disease or date of death in the absence of progression	Event
Either no tumour assessment at baseline or no evaluable assessments post-baseline AND death prior to second scheduled post-baseline disease assessment	Date of death	Event
Either no tumour assessment at baseline or no evaluable assessments post-baseline AND no death prior to second scheduled post-baseline disease assessment	Date of first dose (Day 1)	Censored
Progressive disease or death (in the absence of progression) immediately after $\geq 2$ consecutive missed disease assessments as per the protocol specified assessment schedule	Last evaluable progression-free disease assessment prior to missed assessments (if available). Otherwise, the date of censoring is Date of first dose (Day 1)	Censored
On-going with neither progressive disease nor death at the time of analysis or lost to follow-up or withdrawn consent	Date of last evaluable disease assessment	Censored

PFS = progression-free survival

The PFS time is always derived based on scan/assessment dates, and not on visit dates.

RECIST v1.1 assessments/scans contributing towards a particular visit may be performed on different dates. The following rules are applied:

- The date of progression is determined based on the earliest of the dates of the component that triggered the progression.
- When censoring a participant for PFS the participant is censored at the latest of the dates contributing to a particular overall visit assessment.

Note: for TLs only the latest scan date is recorded out of all scans performed at that assessment for the TLs and similarly for NTLs only the latest scan date is recorded out of all scans performed at that assessment for the NTLs.

The number of participants alive and progression free at 3, 6, 9 and 12 months (PFS-3, PFS-6, PFS-9, and PFS-12) is defined as the Kaplan-Meier estimate of PFS at 3, 6, 9 and 12 months.

‘Potential’ duration of follow-up for PFS is applicable only for PFS censored participants and is defined as follows:

$$\text{Potential duration of follow up for PFS (Months)} = \frac{\text{(Date of PFS censoring-date of first dose of IP)} + 1}{\left(\frac{365.25}{12}\right)}$$

#### **4.2.6.3 Handling of dropouts and Missing Data**

See section [4.2.6.2](#).

#### **4.2.6.4 Analysis of the Secondary Endpoint**

The main analysis of PFS is based on the safety analysis set. The number and percentage of participants experiencing a PFS event broken down by type of event/censoring and Kaplan-Meier plots of PFS are presented. The median PFS and its two-sided 90% CI are estimated using the Kaplan-Meier method if participant numbers allow.

The treatment status at progression of participants at the time of analysis are summarised. This includes;

- The number (%) of participants who were on treatment at the time of progression
- The number (%) of participants who discontinued IP prior to progression
- The number (%) of participants who have not progressed and were on treatment or discontinued treatment.

A summary of the duration of follow-up for PFS is included using median (range). This is presented for censored participants (including all types of PFS censoring).

The proportion of participants alive and progression free at 3, 6, 9 and 12 months and associated two-sided 90% CI are estimated using the Kaplan-Meier method.

#### **4.2.7 Secondary Endpoint: Change in Target Lesion Tumour Size**

Change in TL tumor size is a secondary endpoint.

##### **4.2.7.1 Definition**

This is based on RECIST v1.1 TL measurements taken at baseline and each post-baseline assessment. Tumour size is the sum of the longest diameters (or short axis measurements for

lymph nodes) of the TLs. Baseline for RECIST v1.1 is defined to be the last evaluable assessment prior to first IP dose.

An outcome endpoint for this study is percentage change from baseline in TL tumour size at each post-baseline assessment e.g., at Study week 15.

The tumour size and percentage change from baseline in the sum of tumour size at each assessment are calculated. The best change in tumour size from baseline (i.e., depth of response) is the largest decrease from baseline or the smallest increase from baseline in the absence of a reduction and includes all assessments:

- up to and including the first visit at which the overall visit response is progressive disease,
- prior to death in the absence of progression,
- prior to the start of subsequent anti-cancer therapy (including radiotherapy)
- or up to and including the last evaluable RECIST v1.1 assessment if the participant has not died, progressed, or started subsequent anti-cancer therapy.

Each post-baseline disease assessment for a participant that meets the following conditions are included: all TLs identified at baseline have measurements recorded at the current visit (i.e., they cannot be not done or not evaluable). If a lesion is recorded as  $\leq 5$ mm then this is used in the calculations.

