Any concurrent chemotherapy, radiotherapy, immunotherapy, or biologic or hormonal therapy for cancer treatment other than those under investigation in this study	Should not be given concomitantly while the participants are on study intervention, unless specified in a Substudy. (Concurrent use of hormones for non-cancer-related conditions [eg, insulin for diabetes and hormone replacement therapy] is acceptable. Local treatment of isolated lesions for palliative intent may be acceptable [eg, by local surgery or radiotherapy]) upon consultation with study physician.	
Live attenuated vaccines	Should not be given through 30 days after the last dose of study intervention	
Immunosuppressive medications including, but not limited to, systemic corticosteroids at doses exceeding 10 mg/day of prednisone or equivalent, methotrexate, azathioprine, and tumour necrosis factor-α blockers	Should not be given concomitantly or used for premedication prior to the immunotherapy infusions. The following are allowed exceptions: Use of immunosuppressive medications for the management of study intervention-related AEs Short-term premedication for participants receiving combination agent where the prescribing information for the agent requires the use of steroids for documented hypersensitivity reactions Use in participants with contrast allergies In addition, use of inhaled, topical, and intranasal corticosteroids is permitted A temporary period of steroids will be allowed if clinically indicated and considered to be essential for the management of non-immunotherapy related events experienced by the participant (eg, chronic obstructive pulmonary disease, radiation, nausea, etc)	
Metformin	Metformin has been shown to induce GDF15 gene expression, thereby elevating circulating GDF15 levels significantly. One study showed that a one-time dose of metformin increased mean circulating GDF15 levels about 2.5-fold (Coll et al, 2020). To prevent falsely high GDF15 level results, participants must not take metformin for at least 72 hours prior to the screening GDF15 blood sample and should be switched to an acceptable alternative; the participant must demonstrate controlled diabetes mellitus on this	

Table 8 Prohibited Concomitant Medications

Prohibited Medication/Class of Drug	Usage	
	alternative at least 7 days prior to starting the study intervention on Cycle 1 Day 1.	
Herbal and natural remedies	Should not be given concomitantly unless agreed by the Sponsor	

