This section defines the criteria used to determine objective tumour visit response for RECIST v1.1-defined TLs. The imaging modality, location, and scan date of each TL identified previously at baseline should be documented at follow-up visits with the long axis diameter for non-nodal lesions or short axis diameter for lymph node lesions. All measurements should be recorded in millimeters. The sum of the diameters for all TLs at each follow-up visit will be compared to the baseline sum of diameters (for response or stable disease) or to the smallest prior (nadir) sum of diameters (for progression).

Special cases for TL assessment at follow-up:

- If a lesion has completely disappeared, the diameter should be recorded as 0 mm. If a lesion appears in the same location on a subsequent scan, it will be recorded as an NL.
- If a TL splits into 2 or more parts, the sum of the diameters of those parts should be recorded.
- If 2 or more TLs merge, then the sum of the diameters of the combined lesion should be recorded for 1 of the lesions and 0 mm recorded for the other lesion(s). If the merged TLs are non-nodal lesions, record the long axis diameter of the merged lesion. If pathologic lymph nodes coalesce and are no longer individually separable within a conglomerate mass, the vector of the longest diameter of the coalesced mass should be used to determine the perpendicular vector for the maximal short axis diameter.

- If a TL is believed to be present and is faintly seen but too small to measure, a default value of 5 mm should be assigned. If an accurate measure can be given, this should be recorded, even if it is below 5 mm.
- If a TL cannot be measured accurately due to it being too large, provide an estimate of the size of the lesion. The choice of "Too large to measure" in the case report form will trigger an overall visit response of progressive disease.
- When a TL has had any intervention (eg, definitive radiotherapy, embolization, surgery, transarterial chemoembolization, etc.) during the study, the size of the TL should still be provided where possible and the intervention recorded in the RECIST v1.1 case report form for the current imaging visit and all subsequent visits. If a TL has been completely removed (surgery) or disappears, the longest diameter should be recorded as 0 mm.

Table 24 RECIST v1.1 Evaluation of Target Lesions

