#### 4.2.7.2 Derivations

For visit based summaries, whenever TL tumour size data for each post-baseline assessment (note: or visit at which progression was documented if before the post-line visit) is available then this is used in the analysis. A windowing rule is applied and follows the protocol allowed visit window; therefore, any RECIST v1.1 scan performed within Study W6(D1-D7), W15(D1-D7), W24 $\pm$ 6D then Q9W $\pm$ 6D until W52, then Q12W $\pm$ 6D of the protocol scheduled visit is used for that visit.

The percentage change from baseline in TL tumour size at each post-baseline assessment is obtained for each participant taking the difference between the sum of the TLs at each post-baseline assessment and the sum of the TLs at baseline divided by the sum of the TLs at baseline times 100. For example, the percentage change from baseline in TL tumour size for the post-baseline visit at study week 15 is calculated as follows:

$$\text{Percentage change from baseline in TL tumour size} \\ = \frac{(\text{Study Week 15} - \text{Baseline})}{(\text{Baseline})} \times 100$$

For best percentage change, if it cannot be calculated due to missing data (including if the participant has no TLs at baseline), a value of +20% is imputed as the best percentage change from baseline in the following situations (otherwise best percentage change is left as missing):

- If a participant has no post-baseline assessment and has died;
- If a participant has new lesions or progression of NTLs or TLs;
- If a participant has withdrawn due to progressive disease and has no evaluable TL data before or at progressive disease.

For the outcome endpoint percentage change from baseline in TL tumour size at each post-baseline assessment i.e., Study week 15, participants who progress before study week 15 should have had a tumour assessment performed at the time of progression prior to treatment discontinuation. The tumour size from their latest progression assessment is used instead of the study week 15 assessment for these participants.

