### **Irradiated lesions/lesion intervention**

Previously irradiated lesions (i.e., lesion irradiated prior to entry into the study) are recorded as NTLs and should not form part of the TL assessment.

Any TL (including lymph nodes), which has had intervention during the study (for example, irradiation / palliative surgery / embolization but note this does not include protocol specified biopsies), are handled in the following way. Once a lesion has had intervention then it is treated as having intervention for the remainder of the study noting that an intervention most likely shrinks the size of tumours:

- Step 1: the diameters of the TLs (including the lesions that have had intervention) are summed and the calculation is performed in the usual manner. If the visit response is progressive disease, this remains as a valid response category.
- Step 2: If there is no evidence of progression after step 1, treat the lesion diameter (for those lesions with intervention) as missing. If progressive disease has not been assigned, then the visit response is set as NE.

At subsequent visits, the above steps are repeated to determine the TL and overall visit response. When calculating the previous minimum, lesions with intervention are treated as missing.

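### By-visit tumour-size change and the spider plots can count a resected or locally treated target lesion as shrinkage at a visit whose target-lesion response is not evaluable

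*SAP*

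**What the plan says.** **Which visits count for tumour size.** SAP 4.2.7.1 includes a post-baseline assessment when "all TLs identified at baseline have measurements recorded at the current visit (i.e., they cannot be not done or not evaluable". SAP 4.2.7.2 adds for visit-based summaries that "whenever TL tumour size data for each post-baseline assessment" exists it "is available then this is used in the analysis".

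**How treated lesions are recorded.** Protocol Appendix F (special cases at follow-up) asks sites to go on giving a size where they can after an intervention, and to record the intervention on the RECIST form. It adds: "If a TL has been completely removed (surgery) or disappears, the longest diameter should be recorded as 0 mm".

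**How treated lesions enter response.** SAP Appendix A (irradiated lesions/lesion intervention) covers irradiation, palliative surgery and embolisation. Step 1 calculates with the recorded diameters and lets progression stand. Step 2, if there is no progression, is to "treat the lesion diameter (for those lesions with intervention) as missing", and the visit becomes NE. This lasts for the rest of the study and also governs the previous minimum.

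**Where best change stops.** "The best change in tumour size from baseline (i.e., depth of response) is the largest decrease from baseline" (or the smallest increase), over assessments that include those "prior to the start of subsequent anti-cancer therapy (including radiotherapy"). These stopping points define best change only.

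**Whether such treatment can occur.** Protocol 6.5, Table 8: "Local treatment of isolated lesions for palliative intent may be acceptable", with local surgery and radiotherapy as examples, after consultation with the study physician.

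**The concern.** One visit can be unusable for response and still usable for tumour size. The outputs exposed are the by-visit summaries (study week 15 among them), the waterfall at 15 weeks planned in Protocol 9.4.3 and the spider plots in SAP 4.2.7.3. Protocol 7.1 continues efficacy evaluation after treatment stops, so scans after a local intervention can exist.

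The cohorts are small and uncontrolled: about 10 per tumour type and dose level in Part B, and up to 40 per expansion in Part C. A reader uses these plots to judge whether the drug shrinks tumours. A bar or line driven by a surgeon looks the same as one driven by AZD8853. The SAP accepts this distinction elsewhere: 4.2.2.1 separates surgical from drug-only responses for ORR in colorectal cancer. Tumour size has no counterpart.

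**Working it through.** The plan states no figure to reproduce. The check sets the rules side by side and then applies the plan's formula to assumed lesion sizes.

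**Step 1: does a treated lesion pass the 4.2.7.1 condition?**
- The condition fails only for lesions not done or not evaluable.
- A resected lesion has a recorded 0 mm, and an irradiated or embolised one normally has a recorded size. Both pass on a literal reading.
- SAP Table 10 lists three separate grounds for NE: not assessed, not evaluable, and lesion intervention. The exclusion in 4.2.7.1 matches the first two and leaves out the third.
- 4.2.7 has no cross-reference to the intervention rule.

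**Step 2: which outputs have another stop?**

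| Output | Stop at subsequent anti-cancer therapy | Intervention rule |
|---|---|---|
| Best change, its summary and waterfall | Yes, radiotherapy included | None stated |
| By-visit change, including week 15 | None stated | None stated |
| Week-15 waterfall | None stated | None stated |
| Spider plots | None stated | None stated |

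Curative surgery is identified from the subsequent cancer therapy form (SAP Appendix A, note to Table 13), so it also stops best change.

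**Step 3: illustration.** Formula (SAP 4.2.7.2): change = 100 × (visit sum − baseline sum) / baseline sum. Assumed target lesions are 40 and 30 mm (baseline sum 70 mm), with the 40 mm lesion resected before week 15.
- Other lesion stable: sum = 0 + 30 = 30; 100 × (30 − 70)/70 = **-57.1%**.
- Other lesion grown to 35 mm: 100 × (35 − 70)/70 = **-50.0%**, although the only untreated lesion grew by 5/30 = 16.7%.
- Appendix A for both: Step 1 shows no progression, since 30 and 35 are below the baseline sum. Step 2 makes the 40 mm lesion missing, so the target-lesion response is **NE**.

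**Step 4: when is the -30% reference line reached?** If lesions making up a share *s* of the baseline sum are removed and the rest is stable, the change is −100*s* %. The line is reached at *s* ≥ 0.30. One of five equal lesions removed gives -20%; a sole target lesion removed gives -100%.

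**Step 5: effect on a visit mean.** Assume one retained visit at -57.1% and every other participant at +10%; the mean would be +10.0% if that visit were left out.
- n = 10: (9 × 10 − 57.1)/10 = +3.3%
- n = 20: (19 × 10 − 57.1)/20 = +6.6%
- n = 40: (39 × 10 − 57.1)/40 = +8.3%

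I have not computed an effect on the median, which depends on how the other values are spaced.

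**The case against.** **Depth of response is already protected.** A reader might infer that the whole endpoint, best change included, counts local treatment as drug effect. The documents do not support that. Best change stops at subsequent anti-cancer therapy, radiotherapy is named, and curative surgery comes from the subsequent-therapy form. What remains for best change is palliative surgery or embolisation of a target lesion that is not recorded as subsequent therapy. The documents do not say how these are classified. This objection stands and confines the firm finding to the by-visit outputs.

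**By-visit data are not wholly without limits.** Protocol tumour assessments run until progression, and 4.2.7.2 uses the progression assessment for participants who progress before week 15. That is correct, but neither feature deals with an intervention or with later therapy.

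**A programmer might already exclude these visits.** A diameter treated as missing could be read as failing the 4.2.7.1 condition. That reading is possible, but the SAP does not state it and Table 10's separate listing points the other way. Two programmers could produce different plots.

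**The route is narrow.** Table 8 permits local treatment only after consultation, Table 9 describes palliative radiotherapy as directed at non-target lesions, and anticipated major surgery is an exclusion. This stands as a reason to expect few cases. Table 8 itself is not limited to non-target lesions, and Appendix A provides for treated target lesions.

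**Consequence is limited.** The endpoint is secondary and descriptive, there are no formal hypotheses, and response already applies the NE rule. This also stands.

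**Conclusion.** The gap is real for by-visit percentage change (including study week 15 and its waterfall) and for the spider plots. There, a resected or locally treated target lesion can appear as shrinkage at a visit whose target-lesion response is NE. For best change only the residual gap described above remains. The main ORR analysis is not affected by this omission.

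The size of the bias cannot be estimated, because the documents give no frequency of target-lesion interventions. The -57.1% and the shifts in the mean rest on assumed lesion sizes, one affected participant and +10% in all the others. They show what one case can do and do not forecast how many there will be. The conclusion also assumes that sites record sizes as Appendix F asks, and that Step 1 of the intervention rule does not yield progression.

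**What to change.** Add to SAP 4.2.7.1:

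> From the first intervention on any TL, that lesion's diameter is treated as missing and the visit tumour size is not included, unless the TL sum including the treated lesion itself meets the progressive disease criteria (Appendix A, Step 1). Progression by new or non-target lesions alone does not restore the value.

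The last sentence is needed. If the exception covered any progressive-disease visit, the participant in the illustration who progressed through a new lesion would keep the -57.1%, and 4.2.7.2 could then carry it into week 15.

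Apply the rule to best change, to by-visit change (including the progression-visit substitution for week 15) and to the waterfall and spider plots. Apply the existing subsequent anti-cancer therapy cut-off to the by-visit summaries and spider plots as well as to best change.

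The cost is a short SAP amendment and a programming flag, since interventions are already captured on the RECIST form. The downside is that a few visits become missing.

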#### 4.2.7.2 Derivations

For visit based summaries, whenever TL tumour size data for each post-baseline assessment (note: or visit at which progression was documented if before the post-line visit) is available then this is used in the analysis. A windowing rule is applied and follows the protocol allowed visit window; therefore, any RECIST v1.1 scan performed within Study W6(D1-D7), W15(D1-D7), W24 $\pm$ 6D then Q9W $\pm$ 6D until W52, then Q12W $\pm$ 6D of the protocol scheduled visit is used for that visit.

The percentage change from baseline in TL tumour size at each post-baseline assessment is obtained for each participant taking the difference between the sum of the TLs at each post-baseline assessment and the sum of the TLs at baseline divided by the sum of the TLs at baseline times 100. For example, the percentage change from baseline in TL tumour size for the post-baseline visit at study week 15 is calculated as follows:

$$\text{Percentage change from baseline in TL tumour size} \\ = \frac{(\text{Study Week 15} - \text{Baseline})}{(\text{Baseline})} \times 100$$

For best percentage change, if it cannot be calculated due to missing data (including if the participant has no TLs at baseline), a value of +20% is imputed as the best percentage change from baseline in the following situations (otherwise best percentage change is left as missing):

- If a participant has no post-baseline assessment and has died;
- If a participant has new lesions or progression of NTLs or TLs;
- If a participant has withdrawn due to progressive disease and has no evaluable TL data before or at progressive disease.

For the outcome endpoint percentage change from baseline in TL tumour size at each post-baseline assessment i.e., Study week 15, participants who progress before study week 15 should have had a tumour assessment performed at the time of progression prior to treatment discontinuation. The tumour size from their latest progression assessment is used instead of the study week 15 assessment for these participants.

